For patients who lack the capacity to consent, the investigator/designee may explain the study to the legally authorized representative by phone. The discussion will be documented in the subject's medical record or research chart. Two copies of the unsigned consent form will be sent to the subject/legal representative with instructions for completion of the signature page and assent (if applicable). Signatures will be obtained according to standard Baylor IRB regulations. The subject will be told to keep one form and returned the other to the investigator by mail, email, or fax. The Baylor Investigator/designee will sign the consent form when returned from the subject. The signed consent form will be maintained in research records.

E3. Pregnant woman/fetus

Will pregnant women and/or fetuses (as described in 45 CFR 46 Subpart B) be enrolled in the research?

No

E4. Neonates

Will neonates of uncertain viability or nonviable neonates (as described in 45 CFR 46 Subpart B) be enrolled in the research?

No

E5. Children

Will children be enrolled in the research?

No

Section F: Design/Procedure

F1. Design

Select one category that most adequately describes your research:

c) Pilot

Discuss the research design including but not limited to such issues as: probability of group assignment, potential for subject to be randomized to placebo group, use of control subjects, etc.

Phase I: 20 subjects with COVID-19 infection that are being treated in the hospital. This means that this patient population is positive to COVID-19, are hospitalized, or develop severe symptomatology, but they have been admitted with no more than 48 hours to the hospital. Also, in some cases the patients will not be able to consent at the time of enrollment determines a high grade of severity of illness. The entire cohort will receive daily electrical stimulation in lower extremity (e.g. Gastrocnemius, tibial anterior muscle) up to 1 hour to decrease Neuromyopathy complications and prolonged hospital stay. Due to the condition of the patient we are looking to reduce the interaction with staff, the device will be placed with no additional requirements. Physical therapy targets other physical performances, this device is aimed to improve blood flow, tissue perfusion and muscle activation while the patient is non-responsive to physical activities.

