The protocol will consist of 4 weeks of lower-extremity electrical stimulation. Opposite to our initial study, this modality will consist of home-based therapy, meaning that the patient will take the device home and attend the clinic once a week for screening and assessment of therapy.

The protocol will be performed as the following description: This trial will have 20 patients divided in two groups. Group 1 (intervention, n=10): Will receive an active Tennant Biomodulator Group 2 (control, n=10): Will receive an inactive Tennant Biomodulator This study will consist of 5 visits total and one phone interview 12 weeks after baseline for both groups. The patient will be compensated \$50 per visit (total \$250), with free parking. Payment will only be available for subjects who participate in Part II.

During the first and last visit, the research staff will turn the Tennant Biomodulator PRO® on for one hour and measure any changes in muscle strength, endurance, and blood flow after the therapy. Once the first visit is over, the patient will take the Tennat Biomodulator® home and will be instructed to turn it on for one hour every day for four weeks.

The visits in-between will be performed in the following order: 1) Questionnaires (pain, weakness, sleep, quality of life, frailty, depression, life and space, beck anxiety scale, Katz-daily living) 2) Musculoskeletal assessments (non-invasive surface electromyography, vibration perception threshold) 3) Vascular assessments (non-invasive Near infra-red spectroscopy)

After 4 weeks, the patients will turn back the device to the research staff.

The supervision of this study will be by pulmonary care specialists, and the location will be at the recently open COVID-19 clinic at Baylor College of Medicine.

Section G: Sample Size/Data Analysis

G1. Sample Size

How many subjects (or specimens, or charts) will be used in this study?

Local: 40 Worldwide: 40

Please indicate why you chose the sample size proposed:

Sample size is convenient and selected based on available resources to demonstrate feasibility and the proof of concept effectiveness of EE therapy for COVID-19 patients admitted to ICU and post-ICU. We plan to recruit 40 eligible subjects.

G2. Data Analysis

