Provide a description of your plan for data analysis. State the types of comparisons you plan (e.g. comparison of means, comparison of proportions, regressions, analysis of variance). Which is the PRIMARY comparison/analysis? How will the analyses proposed relate to the primary purposes of your study?

P-values of 0.05 or less will be considered statistically significant based on a two-sided test unless otherwise noted. All variables will be tabulated descriptively at each scheduled time point (baseline and discharge date). For each continuous variable, the analyses will include the mean, standard deviation, minimum and maximum. For each categorical variable, the summary will include frequencies and percentages. Each variable will be analyzed using all available data. Baseline variables will be summarized using descriptive statistics. We assume that a successful intervention is also helpful to maintain subjects muscle mass, reduce neuromyopathy signs and increase venous return flow. The measured parameters (e.g. muscle circumference, sEMG, kent imaging, doppler, etc.) should change substantially from baseline to the end of the intervention. For example, the EMG amplitude values should show increased voltages. Next, for all continuous variables, pre-treatment scores will be regressed on post-treatment scores to form residualized change scores (e.g. sEMG, VPT, dynamometer, etc). Correlations will then be generated among these scores to determine whether changes in sEMG factors are related appropriately with increases in (clinically assessed) functional capacities and self-report measures of activities. ANOVA test will be used to examine significant difference between patients with severe risk factors for prolonged ICU stage (e.g. age, BMI, cardiovascular morbidities). Moderator effects will also be examined for exploratory purposes. Using gender as an example, mixed design ANOVAs will be conducted to determine whether mobility factors change over

the course of treatment at different rates or with different patterns for men and women. Additional analyses will test whether changes in muscle strength and neuropathy (e.g. VPT and dynamometer assessment at time of discharge).

Section H: Potential Risks/Discomforts

H1. Potential Risks/Discomforts

Describe and assess any potential risks/discomforts; (physical, psychological, social, legal, or other) and assess the likelihood and seriousness of such risks:

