Describe potential benefit(s) to be gained by the individual subject as a result of participating in the planned work.

There is potential benefit of prevention or improvement of hospital acquired weakness due to prolonged hospital stay for participants, based on previous studies the electrical stimulation will improve blood flow, tissue perfusion and muscle activation. The device is used to reduce pain. However, the proposed treatment may assist in preventing or improving hospital-acquired Weakness because of prolonged hospital stay . In addition, the participation in this study may help the investigators better understand how COVID19 may impact cause myopathy and neuropathy and how to best help these patients to recover from prolonged hospital-stay .

Primary outcomes include neuropathy (assessed using VPT test); muscle function (assessed using sEMG), and tissue oxygenation (assessed using Kent Imaging). Secondary outcomes include weakness (assessed using dynamometer); muscle atrophy (assessed by weight loss as well as measuring ankle, calf, and thigh circumference); venous return flow (Doppler US [optional]); frailty (frailtymeter [optional]); hospital length of stay (patient medical record); and major adverse events (patient health record). The primary and secondary outcomes will be assessed at baseline (if feasible) and on biweekly basis up to 4 weeks or hospital discharge, whichever came first. Appropriate mixed models (linear for continuous or Generalized Estimating Equations (GEEs) for non-continuous or non-parametric variables) will be used to test the intervention effect for each of the primary (e.g., tissue perfusion, tissue oxygen delivery, neuropathy severity, and

myopathy incident) or secondary (e.g., frailty, weight loss, MAE, etc) outcomes.

Also, participation may help the investigators design a practical assessing method to identify the impact of neuromyopathy in the hospital setting. This may allow physicians to provide personalized care by monitoring muscle loss and limb complications caused by prolonged hospital length of stay.

Describe potential benefit(s) to society of the planned work.

As described above, this type of work may allow physicians to provide more personalized care for hospitalized patients in need of physical therapy for continuous and prolonged periods, specially when having a severe illness that includes medical staff risk contact.

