Title: Electrical Stimulation Therapy for Preventing Hospital-acquired Weakness in Critically Ill COVID-19 Patients - A Proof of Concept Randomized Controlled Trial

Identifier: NCT04685213

Date: May 21, 2021

Statistical analysis plan

Shapiro-Wilk test ($p > 0.05$) was used to assess the normality of data. Independent t-test was used for group comparison at baseline on normally distributed continuous demographics, clinical data, and sEMG parameters. Mann-Whitney U test was used if the assumption of normal distribution was not satisfied. For categorical variables, Chi-square test was used to compare between-group differences at baseline. The effect size for baseline continuous and categorical data were measured using Cramer's V and Cohen's d, respectively. Generalized estimating equations (GEE) was used to test the main effect of group (two levels: CG and IG), time (three levels: baseline, 3 days, and 9 days), and their interaction on the outcome measures regardless of data unable to obtain due to the patients' critical condition. Pearson correlation was used to associate baseline values with %change of outcomes at 9 days. For those significant associations, multiple linear regression was used to determine the relationship between those significantly associated variables. The model performance was reported in terms of variance (R^2), and p-value. For all tests, an alpha level of < 0.05 was considered statistically significant.

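### The SAP's GEE does not say which term is the treatment effect, states no small-sample variance correction, and gives up baseline precision when visit correlation is low to moderate

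*SAP*

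**What the plan says.** The SAP's single analysis paragraph lists three GEE tests: the main effect of group (control and intervention), the main effect of "time (three levels: baseline, 3 days, and 9 days), and their interaction on the outcome measures". None is designated as the efficacy result. Day 9 is singled out only later, in the correlation of baseline values with percentage change. No working correlation, variance estimator or reference distribution is given. The significance rule is general: "For all tests, an alpha level of < 0.05 was considered statistically significant". Missing data are covered only by the remark that the model was used "regardless of data unable to obtain due to the" patients' critical condition.

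The protocol does not fill the gap. Section I says that linear mixed models (continuous outcomes) or GEE (other outcomes) "will be used to test the intervention effect for each of the primary" and secondary outcomes, again without a term, contrast or visit. Section G2 sets a two-sided rule: "P-values of 0.05 or less will be considered statistically significant based on a two-sided test unless otherwise noted".

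On allocation, the SAP title calls the study "A Proof of Concept Randomized Controlled Trial". Protocol section F1 gives the hospital phase no comparison group: "The entire cohort will receive daily electrical stimulation in lower extremity". Section F2, Phase II, is the only place with two arms, 10 active and 10 inactive: "This trial will have 20 patients divided in two groups". It describes no randomisation procedure. Section G1 gives 40 patients in total.

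**The concern.** Two terms in the model involve group, and they answer different questions. The group main effect pools a visit at which treatment cannot have acted. The interaction is where the effect sits, but with three time levels its test has no direction, no single estimate and no confidence interval. A reader of a significant result could not tell whether day 3, day 9 or both carried it.

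Two further choices matter in a study this small. The ordinary GEE sandwich variance is too small with few clusters, so p-values come out too low. A separate baseline mean for each group makes the day-9 contrast an unadjusted difference in change, which is less precise than an analysis using the baseline as prior information unless visits are very highly correlated. At stake are the error rate behind any claim of significance and the width of the interval that a proof-of-concept study exists to provide.

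**Working it through.** The documents state no power, precision or sample-size figure, so there is none to reproduce.

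**Inputs from the documents.** Two groups and three visits including baseline (SAP); alpha 0.05 (SAP), two-sided (protocol G2).

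**Assumptions.** Complete Gaussian data, equal SDs, common between-visit correlation r. Arm size is 10, borrowed from Phase II, or 20, the largest equal split of 40 patients.

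**1. What each term estimates.** Let the true effects be 0 at baseline, d3 at day 3 and d9 at day 9.
- Group main effect, averaged over visits: (0 + d3 + d9)/3. With d3 = 0.5 SD and d9 = 1 SD it is 1.5/3 = 0.50 SD; with both at 1 SD it is 0.67 SD.
- Group coefficient with baseline as the reference level: the baseline difference alone, with expectation 0 under randomisation.
- Group-by-time: the pair (d3, d9), tested jointly on 2 df.

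**2. Null rejection at nominal 5%.** With complete data, the free-baseline GEE estimates are differences in cell means. They were tested with the uncorrected sandwich (z or chi-square reference) and with a Mancl-DeRouen correction (t or F reference). Rates are for r between 0.3 and 0.9, with 40,000 simulated trials per setting.

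| Test | 10 per arm, uncorrected | 20 per arm, uncorrected | 10 per arm, corrected |
|---|---|---|---|
| Day-9 contrast | about 8% | about 6% | about 4% |
| Group main effect | about 8% | about 6% | about 4% |
| 2-df interaction | about 11% | 7% to 8% | 4% to 5% |

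**3. Precision of the day-9 contrast.** Variances are in units of 2 SD²/n.
- Free baseline (difference in change): 2(1 − r).
- Common baseline: (1 − r²)(1 + 1/(N − 4)). With N = 20 the last factor is 1 + 1/16 = 1.0625, the cost of estimating the adjustment.
- Ratio: 1.0625 × (1 + r)/2, which equals 1 at r = 0.88.

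| r | Free | Common | Variance lower by | Power for 1 SD |
|---|---|---|---|---|
| 0.3 | 1.40 | 0.967 | 31% | 43% to 57% |
| 0.5 | 1.00 | 0.797 | 20% | 56% to 66% |
| 0.7 | 0.60 | 0.542 | 10% | 78% to 82% |
| 0.8 | 0.40 | 0.383 | 4% | 92% to 93% |
| 0.9 | 0.20 | 0.202 | none | unchanged |

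Power uses the noncentral t with 18 and 17 df. At r = 0.5 the 95% CI half-width goes from 0.94 SD to 0.84 SD. At 20 per arm the factor is 1 + 1/36, and the reductions at r = 0.3, 0.5, 0.7 and 0.8 are about 33%, 23%, 13% and 7%.

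**4. The working correlation decides whether the gain is realised.** Under independence, the common-baseline estimate at day 9 is simply the post-treatment difference, with variance 1. Its ratio to the free-baseline contrast is 1/(2(1 − r)): 0.71 at r = 0.3, 1.00 at 0.5 and 1.67 at 0.7. The constraint therefore helps reliably only with an exchangeable or unstructured working correlation.

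**The case against.** The strongest reply is that the SAP does list a valid test. Under randomisation the interaction is sound, and modelling baseline as an outcome level is legitimate. A reader might infer that the model itself is wrong; it is not. The faults are the undesignated effect, the unstated variance correction and the unused precision.

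The precision point is also conditional. No r is given, and at 0.7 to 0.8 the power gain is only 4 points and then 1. Protocol F2 has both legs measured. If legs are averaged and their errors are independent (an assumption), r becomes 2r/(1 + r): 0.5 becomes 0.67 and the gain falls from 20% to 11%, 0.7 becomes 0.82 and it falls from 10% to 3%, and at 0.8 it disappears. That stands, so this part is secondary.

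The arm size is borrowed. The 10/10 split belongs to home treatment with weekly visits, while a 3-day and 9-day schedule looks more like the hospital phase, which has no control group in the protocol. Hence the range up to 20 per arm, where the excess rejection is smaller but remains.

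A reader might also infer a false-positive rate near 18%. That is the simulated chance, at 10 per arm and uncorrected, that either the group main effect or the interaction is significant (13% to 14% at 20 per arm). It needs a rule that either term counts, and the SAP states no such rule. Nor do the documents show that the group main effect was read as efficacy. It need not even lack power: with a constant 1 SD effect and r = 0.3, its corrected power is 45%, against 39% for the free-baseline day-9 contrast. The objection to it is what it means.

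Finally, the SAP is written in the past tense, so naming a visit now cannot restore prespecification. That is correct and is reflected in the fix.

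**Conclusion.** The concern holds in a limited form. Two statements need no numerical assumption: the SAP designates no treatment effect among its GEE terms, and the group main effect is not one. The sizes rest on assumptions. With complete Gaussian data, uncorrected tests reject about 8% to 11% at 10 per arm and about 6% to 8% at 20 per arm, against a nominal 5%. The avoidable variance at day 9, at 10 per arm, runs from about 31% at r = 0.3 to nothing near 0.9.

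The documents do not support saying that the reported conclusion is wrong, that the wrong term was used, or that the trial was not randomised. They leave allocation unreconciled: the SAP title asserts randomisation, and the protocol describes no procedure. Because the correction and the baseline adjustment are cheap at any arm size this 40-patient study allows, the change should be made.

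**What to change.** 1. Report the intervention-minus-control group-by-time contrast at one named visit, with a 95% CI, as the treatment effect. Day 9, the last visit, is the natural choice. Do not read the group main effect as efficacy. If the analysis has been done and no earlier document names the visit, label the choice post hoc.
2. Apply a small-sample correction to the sandwich variance, such as Mancl-DeRouen, with a t or F reference.
3. If randomisation is confirmed, constrain baseline means to be equal (time, group-by-day-3 and group-by-day-9, with no group term at baseline), using an exchangeable or unstructured working correlation and not independence. Otherwise keep the free-baseline day-9 contrast with a corrected CI.
4. Data are missing because patients were critically ill, so missingness completely at random is doubtful. For continuous outcomes, consider the linear mixed model already named in protocol section I, fitted by likelihood. It does not need that assumption, though it still needs missingness to be explained by the observed data.

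The cost is SAP wording, one model constraint and one re-run per outcome, with no new patients or data. Some nominally significant results may be lost under the correction. Multiplicity across the several outcomes is a separate matter that this change does not settle.

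### The SAP names critical illness as the reason for missing data but plans nothing for it, so if loss differs between arms the day-9 group contrast can be biased; how death enters that contrast is also unstated

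*SAP*

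**What the plan says.** The SAP's outcome model is a GEE for "group (two levels: CG and IG), time (three levels: baseline, 3 days, and 9 days), and their interaction", fitted "regardless of data unable to obtain due to the patients' critical condition". No working correlation, weighting, imputation, missingness assumption or sensitivity analysis follows. A later step also needs a day-9 value: "Pearson correlation was used to associate baseline values with %change of outcomes at 9 days", with multiple regressions built on the significant correlations.

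The protocol says in G2 (Data Analysis): "Each variable will be analyzed using all available data". Section I (Potential Benefits) is more specific. There, "Appropriate mixed models (linear for continuous or Generalized Estimating Equations (GEEs) for non-continuous or non-parametric variables) will be used" to test the intervention effect, and major adverse events are among the outcomes to be modelled. The same section ends outcome assessment at 4 weeks or at discharge, whichever is earlier, and lists major adverse events as a secondary outcome. F2 (Phase I, Aim 2) counts death among those events and takes them from the health record.

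On numbers, G1 says: "Sample size is convenient and selected based on available resources". It gives no expected loss, SD or effect size.

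**The concern.** Unweighted GEE on the available values is valid in general only when loss is unrelated to the outcome. The SAP itself gives a reason for loss that is plausibly related: muscle function, neuropathy and tissue oxygenation are likely to be worse in patients too ill to be measured. Discharge before day 9 is a second outcome-related reason and acts the other way, removing the fittest.

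The day-9 contrast then compares those who could be measured in each arm. If the sickest controls are lost more often, the control mean improves and the estimate moves against stimulation. If the intervention arm loses more of its sickest patients, the estimate moves in its favour. A patient who died, one too unstable to assess and one who went home all appear as the same blank. The day-9 percent-change correlations, and the regressions that follow, use only patients measured at day 9 and share the problem.

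**Working it through.** There is no figure in the plan to reproduce: the total of 40 is a convenience number with no dropout allowance. The question is how much severity-related loss could move the day-9 contrast.

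**Assumed inputs (none are in the documents).** Outcome SD 1, coded so that higher is better; no true effect; baseline and day 3 fully observed. The true correlation is either exchangeable 0.6 or AR(1) 0.8, so the day-3 to day-9 correlation r is 0.6 or 0.8. Loss at day 9 is 40% in control and 20% in intervention. The chance of loss is *a* if the driving value is below average and *b* if above:

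- intervention: a = 0.30, b = 0.10 (mean 0.20)
- control, milder split: a = 0.60, b = 0.20 (mean 0.40)
- control, steeper split: a = 0.70, b = 0.10 (mean 0.40)

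**Step 1: shift in the driving value among patients still measured.** The two halves of a standard normal have means ±√(2/π) = ±0.798, so the mean among those retained is 0.798 × (a − b)/(2 − a − b).

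- intervention: 0.798 × 0.20/1.60 = 0.100
- control, milder: 0.798 × 0.40/1.20 = 0.266
- control, steeper: 0.798 × 0.60/1.20 = 0.399

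The difference D (intervention minus control) is −0.166 (milder) or −0.299 (steeper).

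**Step 2: loss depends on the observed day-3 value.**

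- Independence GEE uses the raw day-9 means, so the bias is r × D. With r = 0.6: −0.10 and −0.18. With r = 0.8: −0.13 and −0.24.
- Exchangeable working correlation w puts weight w/(1 + w) on each earlier visit, so the bias is D × [r − w/(1 + w) × (r₁₃ + 1)], where r₁₃ is the true baseline to day-3 correlation. With w = 0.6 the weight is 0.375. If the truth is exchangeable 0.6, the bracket is 0.6 − 0.375 × 1.6 = 0, so the bias is 0.00. If the truth is AR(1) 0.8, it is 0.8 − 0.375 × 1.8 = 0.125, so the bias is −0.02 or −0.04.
- Likelihood with the correct covariance: 0.00.

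**Step 3: loss depends on the unseen day-9 value.**

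- Independence GEE: the bias is D itself, −0.17 or −0.30.
- Likelihood with the correct covariance: D × (1 − R²), where R² is the share of day-9 variance explained by the two earlier visits. Exchangeable 0.6: R² = 2 × 0.36/1.6 = 0.45. AR(1) 0.8: R² = 0.64.

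| Control split | Independence | Correct covariance, exchangeable 0.6 | Correct covariance, AR(1) 0.8 |
|---|---|---|---|
| Milder | −0.17 | −0.166 × 0.55 = −0.09 | −0.166 × 0.36 = −0.06 |
| Steeper | −0.30 | −0.299 × 0.55 = −0.16 | −0.299 × 0.36 = −0.11 |

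**Step 4: same loss rule in both arms.** D = 0, so with no true effect there is no bias under any of these models. In simulations with a true effect of 0.50 SD and loss driven by the day-3 value, a common rule gave 0.47 to 0.49.

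**Cross-check.** A simulation with a smooth (logistic, slope 1.5) loss rule, 40% v 20% loss and exchangeable correlation 0.6 gave −0.12 (independence) and 0.00 (exchangeable) when loss depended on day 3. It gave −0.21 and −0.12 when loss depended on day 9. These agree with the figures above.

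**The case against.** The strongest reply is that the harm is conditional. It needs loss to differ between arms, and the documents give no loss rates. The larger figures under day-3-driven loss come from independence working correlation, which the SAP does not specify; a sensible exchangeable structure nearly removes them. The protocol's Section I already plans a linear mixed model for continuous outcomes. All of this stands, and it limits the point to a contrast that can be biased. It does not remove the point: the SAP applies GEE without that distinction and names no working correlation. If patients are missed because of how ill they are on day 9, the better model still leaves bias.

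Three stronger readings are tempting, and the documents do not support them.

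- A reader might infer that deaths disappear from the trial unseen. They do not: the protocol records death as a major adverse event and lists those events as a secondary outcome. The gap is that the SAP neither carries this over nor says how death enters the day-9 analysis.
- A reader might infer arms of about 10 for this comparison. The protocol gives 10 per group only for Phase II, the home-based outpatients. No arm size is stated for an inpatient comparison.
- A reader might infer that replacing GEE with a likelihood model cures the problem. Step 3 shows that it does not when loss depends on the unseen day-9 state.

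**Conclusion.** The concern holds as a risk of bias, not as a demonstrated bias. The SAP identifies critical condition as the cause of missing values and then plans nothing that addresses it. Under an assumed 40% v 20% loss and no true effect, the day-9 contrast moves as follows:

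- Loss driven by day 3: about −0.10 to −0.24 SD with independence GEE, and 0.00 to −0.04 SD with exchangeable.
- Loss driven by day 9, steeper split: about −0.30 SD with independence, and −0.11 to −0.16 SD with the correct covariance. The milder split gives −0.17 SD, and −0.06 to −0.09 SD.

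The sign reverses if the intervention arm loses more of its sickest patients. These sizes rest on assumed loss rates, loss rules and correlations; the actual size and direction cannot be found from the documents. The change is worth making because it is cheap and partly written in the protocol already.

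**What to change.** 1. For continuous outcomes, use the linear mixed model named in the protocol's Section I, fitted by likelihood to all visits. Use an unstructured covariance, with a stated simpler structure as fallback if it does not converge. Where GEE is kept, state a working correlation other than independence. State the missingness assumption in either case.
2. Tabulate missing day-3 and day-9 values by arm and reason: died, too unstable to measure, discharged, withdrew. The SAP is written in the past tense, so if collection is over, take the reasons from the health record.
3. Add one day-9 worst-rank sensitivity analysis, with death ranked worst and too unstable to measure next. State where patients discharged before day 9 are placed. Item 1 alone does not remove bias when loss depends on the unseen day-9 state.
4. Report major adverse events, including death, by arm, and say in the SAP how death is handled in the day-9 comparison.

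The cost is revised SAP wording, refitting the model, a review of records for the reasons and one extra rank analysis. The result may be less favourable.
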